Patients with palliative oesophageal cancer are in most instances frail and have a significantly limited life expectancy. It is thus imperative upon discharge, that further research-related follow-up should not inconvenience the patient nor have a negative effect on their quality of life. Furthermore, many of the patients treated at GSH have limited financial means to afford repeated follow-ups at the hospital. For these reasons, subsequent follow-up after discharge, will be done telephonically. Patients will be phoned at 1, 2, 4 and 8 weeks post stent insertion and will be asked about any symptoms related to the stent insertion, and have an assessment of symptomatic GOR using the GerdQ questionnaire ⁸, dysphagia, cough and pain levels at each telephonic follow-up. Telephonic follow-up of these patients will be done by the Clinical Coordinator, who is blinded to which type of stent the patient has received.

All patients will also be referred to the GSH Palliative Care Team. With any symptom reported by a patient or family member that is deemed to possibly require further intervention or treatment, the patient will be requested to return for an evaluation or appropriately managed according to the Palliative Care Distress Algorithm (Appendix 1). All complications will be managed as per standard treatment routinely employed for such a complication at GSH. Any such complications will be documented.

OUTCOME MEASURES

Primary Outcome Measure

The primary outcome will be patient-reported rates of symptomatic volume GOR and objectively measured volume GOR in both study groups. Patient-reported symptomatic volume GOR will be assessed using the validated GerdQ questionnaire (Appendix 2)⁸. This questionnaire has been chosen has it is simple, easy to understand and includes only 6 questions, which are all reflux-related. This questionnaire will be administered to the patient prior to the procedure, to establish a baseline. It will then subsequently be telephonically administered at the scheduled telephonic follow-ups at weeks 1, 2, 4 and 8. The GerdQ questionnaire enables the patient to provide a score at each follow-up interaction which can then be documented and the mean scores between the two groups can then be compared.

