GOR will also be objectively measured on day 1 post stent insertion using scintigraphy. The proposed protocol for scintigraphy is described in Appendix 3. This modality has been chosen as its accuracy compares favourably to pH monitoring⁹, but is much less invasive. It requires the patient to swallow a meal of soft, runny porridge and then undergo imaging. pH monitoring is invasive, requiring the insertion of an uncomfortable nasal probe which stays in-situ for 24 hours, increasing discomfort for the patient but also increasing the hospital stay by a further 24 hours. It is thus deemed inappropriate in this setting.

Secondary Outcome Measures

The secondary outcomes that will be assessed will include immediate technical success rate and any complications related to the stent insertion, subsequent stent-related complications, patient-reported dysphagia score prior to stent insertion, on day 1 post-insertion and then at each of the scheduled telephonic follow-ups and lastly, patient survival at 2 months post stent insertion. Dysphagia assessment will be done using the modified dysphagia scale first published by Mellow and Pinkas and validated for assessing dysphagia after metal stent insertion for oesophageal cancer (Appendix 4)²³. Furthermore, an assessment of the patient's pain level and whether they are coughing will also be documented, using validated pain²⁴ and cough scores²⁵ and pain (Appendix 5 & 6).

Data Collection

The following data parameters will be collected:

- Age
- Gender
- Performance status25 and BMI of the patient at time of stent placement
- Histological type of malignancy (e.g. adenocarcinoma, squamous cell carcinoma or other)
- Reason for inoperability: metastases, locally advanced or poor performance status
- Position of oesophageal malignant stricture (endoscopic measurement in centimetres from the incisors)
- Patient-reported degree of dysphagia prior to stenting
- Patient-reported GerdQ score pre-stenting
- Stent characteristics: anti-reflux vs conventional, length, diameter and brand name of stent
- Immediate technical success rate
- Immediate stent insertion complications:
 - o Bleeding
 - Perforation
 - o Other

- Subsequent stent-related complications during the follow-up period:
 - o Bleeding
 - Perforation
 - Migration
 - Stent occlusion and cause thereof
 - \circ Other
- Quantitative assessment of volume reflux as per scintigraphy (on day 1)
- GerdQ score at follow-up at week 1, 2, 4 and 8

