This trial will not involve a pharmaceutical product or device that requires repeated administration. Both stents are inserted as a once-off procedure and unless there is an unforeseen complication (such as stent migration or patient intolerance of the stent necessitating removal), these stents usually stay in-situ indefinitely. With the unfortunately short life expectancy for this group of patients, most participants will require a single stent insertion and will then die with the stent still in-situ. This means that once the trial period is over, they will still continue to have the benefit of the stent regardless of when the trial ends. If the anti-reflux stents are proven to significantly reduce GOR, those participants in the conventional stent group will however not be offered an anti-reflux stent if the stent they have received is still functional and without problems. This is because the procedure of exchanging one stent for another carries significant risks and in this vulnerable group of patients such a stent exchange procedure would not be justified.

Statistical Analysis

Data will be captured using the REDCap electronic data capturing software licensed to the University of Cape Town. All data exploration and analysis will be done using an appropriate statistical software programme such as SPSS (version 27.0, IBM, USA). Statistical significance will be set as p <0.05. Recorded data will be expressed as mean (SD), or median (interquartile range) when non-normally distributed (continuous data). Where continuous data are non-normally distributed, variables will be logarithmically transformed prior to inclusion in multivariable statistical analysis. Dichotomous variables will be expressed as proportions or percentages. Baseline demographic and clinical characteristics between the anti-reflux stent and the conventional stent group will be compared using appropriate statistical tests based on the nature of the data as well as distribution thereof. GOR scores between the two groups will be assessed using inferential statistics with the hypothesis that the anti-reflux stent group will have reduced reflux compared to the conventional stent group. In addition, survival analysis will be performed with visual representation using Kaplan Meier curves.

Sample Size

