Appendix 4: Dysphagia Score

Appendix 5: Pain Score – Visual Analog (Face) Score

Appendix 6: Simplified Cough Score

Appendix 7: Proposed Data Sheet

Appendix 1 : Palliative Care Distress Management Algorithm

Appendix 2: GerdQ score⁸

Frequency score (points) for symptom

Question	0 day	1 day	2–3 days	4–7 days	
1. How often did you have a burning feeling behind your breastbone (heartburn)?	0	1	2	3	
2. How often did you have stomach contents (liquid or food) moving upwards to your throat or mouth (regurgitation)?	0	1	2	3	
3. How often did you have a pain in the centre of the upper stomach?	3	2	1	0	
4. How often did you have nausea?	3	2	1	0	
5. How often did you have difficulty getting a good night's sleep because of your heartburn and/or regurgitation?	0	1	2	3	
6. How often did you take additional medication for your heartburn and/or regurgitation, other than what the physician told you to take? (such as Tums, Rolaids, Maalox?)	0	1	2	3	

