Appendix 4: Dysphagia Score²³

- 0 = normal/no dysphagia
- 1 = ability to eat some solid food
- 2 = ability to eat semisolids only
- 3 = ability to swallow liquids only
- 4 = complete dysphagia (inability to swallow saliva)

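### The rule to log-transform non-normal variables has no answer for zeros, which are the best results on scintigraphic reflux and, if treated as continuous, on the dysphagia and cough scores

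*Combined protocol and SAP*

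**What the plan says.** The Statistical Analysis section of the combined protocol and SAP states the rule in one sentence: for continuous data that are non-normal, "variables will be logarithmically transformed prior to inclusion in multivariable statistical analysis". The multivariable analysis is not described further, and no variables or outcomes are listed for it.

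The reflux comparison is described separately and only in general terms: "GOR scores between the two groups will be assessed using inferential statistics". For GerdQ, the Primary Outcome Measure section adds that "the mean scores between the two groups can then be compared".

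The measures that concern us are these:

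- **Scintigraphy**, the objective half of the primary outcome, is listed under Data Collection as "Quantitative assessment of volume reflux as per scintigraphy (on day 1". Neither that section, Appendix 3 nor the data sheet in Appendix 7 gives a unit or a formula.
- **Dysphagia** (Appendix 4) runs from 0 to 4, with "0 = normal/no dysphagia" as the best grade.
- **Cough** (Appendix 6) runs from 0 to 3 for day and for night, and 0 means no cough.
- **GerdQ** (Appendix 2) has six items of 0 to 3 points. Items 3 ("How often did you have a pain in the centre of the upper stomach") and 4 ("How often did you have nausea") are scored in reverse, so no symptom days earns 3 points on each.

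**The concern.** A log transform suits positive, right-skewed data. Three of this trial's outcomes have, or probably have, a floor at zero that stands for the best result. Measures with many patients at the floor are also the ones most likely to be judged non-normal, which is what triggers the rule.

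Two things can then happen, and the plan does not choose between them. Software may treat the log of zero as missing, so patients leave the model because of a result observed after randomisation. If the valve works by abolishing reflux in some patients, more of them leave the anti-reflux arm, and what remains is a comparison among patients who still reflux. Alternatively, the analyst may add a constant. The estimated effect and its p-value then depend on a number that is not in the plan, chosen by a team that the Trial Design section says is not blinded to stent type.

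**Working it through.** **1. The plan's own figure.** The Sample Size section compares GerdQ means of 9 and 7, SD 3, alpha 5%, power 80%. Per arm, n = 2 × (1.960 + 0.842)² × 3² / 2² = 2 × 7.85 × 2.25 = 35.3, rounded up to 36, or 72 in total. This reproduces with a two-sided test on the raw, unlogged scale.

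**2. Can GerdQ be zero?** With no symptom days on any item the total is 0 + 0 + 3 + 3 + 0 + 0 = 6. A total of 0 needs zero points on items 1, 2, 5 and 6, with both upper-stomach pain and nausea on 4–7 days. That is 1 of 4⁶ = 4096 answer patterns, and it is not a symptom-free patient. Under the plan's means and SD (rounded normal), the chance of a score of 0 or below is Φ((0.5 − 9)/3) = 0.0023 and Φ((0.5 − 7)/3) = 0.0151. Expected zeros are 36 × 0.0023 = 0.08 and 36 × 0.0151 = 0.54, about 0.6 of 72 patients. The zero problem is negligible for GerdQ.

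**3. What zeros do on a zero-heavy measure.** The documents give no zero shares or distribution for scintigraphy, so all inputs here are assumed: 36 per arm, a given share of exact zeros, and log-normal positive values with log-SD 1. Patients kept when zeros are dropped, for 20% vs 50% zeros: 36 × 0.80 + 36 × 0.50 = 28.8 + 18.0 = 46.8. For 20% vs 60%: 28.8 + 14.4 = 43.2. For 10% vs 30%: 32.4 + 25.2 = 57.6.

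The table gives the simulated share of runs with p < 0.05, using a two-sample t-test on the log scale (6000 runs for the first two rows, 3000 for the others). Brackets hold the estimated anti-reflux to conventional ratio where it was recorded; a dash means not run.

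| Zeros, conventional vs anti-reflux | Geometric mean of positives | Zeros dropped | c = 0.01 | c = 0.1 | c = 1 | Rank test, all kept |
|---|---|---|---|---|---|---|
| 20% vs 50% | 2.7 in both | 4.7% | 75.1% | – | 55.8% | 63.4% |
| 20% vs 60% | 2.7 in both | 4.6% | 93.4% | – | 79.2% | 87.4% |
| 20% vs 50% | 5 in both | 4.6% (0.989) | 74.9% (0.153) | 71.7% (0.304) | 60.7% (0.568) | – |
| 10% vs 30% | 5 in both | 5.1% (0.999) | 54.3% (0.286) | 47.4% (0.452) | 33.6% (0.687) | – |
| 20% vs 50% | 5 vs 4 | 10.9% (0.801) | 80.8% (0.139) | 79.9% (0.276) | 74.1% (0.525) | – |

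A separate rerun of the first row gave 4.9% with zeros dropped, 74% and 56% for c = 0.01 and 1, and 63% for the rank test.

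**4. Reading the table.** With zeros dropped and equal positives, the test rejects at its nominal 5% and the ratio sits at 1: a difference in the proportion free of reflux is invisible. With a constant, the same data give a ratio anywhere from 0.153 to 0.568 (third row). Changing the measurement unit has the same effect as changing c. Here c = 1 is 1/2.7 = 37% of a typical positive value in the first row but 1/5 = 20% in the third, and rejection moves from 55.8% to 60.7%. Since the protocol fixes no unit, it fixes no meaning for any c.

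**The case against.** The strongest reply is about scope. The rule covers continuous data, and only before multivariable analysis. No multivariable outcome model is specified, so the logged variables might be covariates such as age or BMI. Dysphagia and cough are short ordered categories, which a statistician need not treat as continuous. The rule may therefore never touch an outcome. This stands as a limit on the point: the effect is conditional. It does not dispose of it. For outcomes, the section distinguishes only continuous and dichotomous data, apart from survival, and names no ordinal method. Its promise to choose tests by the nature of the data is made for baseline comparisons. Scintigraphic reflux is described as quantitative and would fall under the rule.

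A reader might go further and infer that symptom-free patients would drop out of the GerdQ analysis, or that the primary GerdQ comparison fails. The documents do not support either. The reverse-scored items put a symptom-free patient at 6, and the GerdQ comparison is of mean scores with no log scale mentioned.

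A reader might also infer bias against the anti-reflux stent on dysphagia. That would need more zeros in that arm, whereas the introduction and the risk section expect similar dysphagia relief with both stents.

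It is also fair to say that the 5% figure is built in by giving both arms the same distribution among positives. With an effect among positives as well (5 vs 4), dropping zeros gives 10.9%, still far below the 74.1% to 80.8% when zeros are kept with a constant. Finally, how a scan without reflux would be recorded cannot be determined from the documents, and the zero point of the pain score cannot be checked because its figure is not shown, so pain is left out.

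**Conclusion.** The point holds in a limited form. As written, the rule cannot be applied to an outcome that contains zeros, and the plan does not say what to do instead. It matters most for scintigraphic reflux, and for dysphagia and cough if they are handled as continuous, in any multivariable analysis of those outcomes.

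Under the assumed 20% vs 50% zero reflux with equal positives, about 25 of 72 patients would be lost and rejection would be about 5%, against about 63% for a rank test and 56% to 74% for log(x + c) with c from 1 to 0.01. These figures show the direction and possible size of the problem; they do not predict this trial's power. They rest on assumed zero shares, a log-normal shape, no reflux being recorded as exactly 0, and an unadjusted test standing in for the unspecified multivariable model. This is worth correcting before analysis, but it does not undermine the sample size or the unadjusted GerdQ comparison.

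**What to change.** Remove the log-transform rule for outcomes and name the method for each:

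- **GerdQ:** analyse on its original scale, which is the scale used for N = 72, adjusted for the baseline GerdQ already collected before stenting. Judge normality on the model residuals, not on the raw scores.
- **Scintigraphic reflux, dysphagia and cough:** use a rank-based or proportional-odds comparison that keeps zeros. For scintigraphy, also state the unit and how a scan with no reflux is recorded.

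The cost is a few sentences in the Statistical Analysis section, with no new data and no change in sample size. The drawback is that the effect for the zero-anchored outcomes would be reported as an odds ratio or a rank measure instead of a ratio of means.

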Oesophageal cancer is an aggressive condition, resulting in the vast majority of patients having evidence of locally invasive, irresectable disease or distant metastases at the time of presentation¹. Overall survival remains poor. Management in the South African setting is plagued by late presentation of these patients², with less than 5% being eligible for curative treatment ^{3,4} and median survival from the time of diagnosis being only 15 weeks⁴, while those who present with complete obstruction having a median survival of only 75 days (10.7 weeks)⁵. Treatment of these patients in the South African setting remains predominantly palliative. The most common and debilitating symptom of advanced oesophageal malignancy is progressive dysphagia¹, which can be addressed by the endoscopic placement of self-expanding metal stents. The major drawback of stenting tumours in the lower oesophagus or oesophagogastric junction (OGJ), is the associated gastro-oesophageal reflux (GOR) resulting from the stent crossing the lower oesophageal sphincter and essentially negating the native anti-reflux mechanism. Significant reflux is the most common complaint worsening quality of life after stent placement in these patients and can be as high as 100% in some series⁶. Prescribing routine proton pump inhibitors (PPIs) or placing stents with built-in anti-reflux mechanisms are methods aimed at reducing this symptomatic reflux ¹.

Diagnosis of GOR in general remains a challenge and numerous diagnostic tests are available. As no specific validation has been done for GOR assessment after placement of oesophageal stents, data on diagnostic techniques of GOR are taken from the primary health care setting or from studies looking at patients who are being considered for, or who have had, anti-reflux surgery. International guidelines, such as the American College of Gastroenterology⁷, propose that typical symptoms of GOR confirm a presumptive diagnosis and should prompt empiric medical management (usually with PPIs). Further special investigations to confirm GOR include upper gastrointestinal endoscopy and ambulatory pH monitoring. Barium radiography and oesophageal manometry are not typically recommended as part of the diagnostic work-up⁷.

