The primary objectives of this trial will be to compare rates of self-reported, symptomatic volume GOR and objectively measured rates of volume GOR using scintigraphy, between the two study groups. This will be a superiority trial, with the hypothesis being that palliative oesophageal anti-reflux self-expanding fully covered metal stents significantly reduce volume GOR compared to conventional oesophageal self-expanding fully covered metal stents.

Secondary Objectives

Secondary objectives will be to compare outcomes, including rates of dysphagia, cough, pain, stentrelated complications, subsequent complications and patient survival at the end of the study period. A further objective will be to compare the self-reported GOR questionnaire (GerdQ) outcomes to the objectively measured oesophageal scintigraphy measurements.

METHODS

Trial Design

This study will be a prospective randomised controlled trial comparing anti-reflux oesophageal stents to conventional oesophageal stents. Randomisation to an anti-reflux stent versus a conventional stent will be done prior to stent placement and the patient will remain blinded to the type of stent placed. Although the authors will not be blinded to the stent type, as the stents are easily distinguished from each other at the time of endoscopy, the Clinical Coordinator who will be doing the follow-up will be blinded to this. This study will be performed following the CONSORT 2010 checklist of information for randomised trials ²².

Once the study is approved by the University of Cape Town's Human Research Ethics Committee, approval for the study will also be obtained from Groote Schuur Hospital. The trial will then be registered with the South African National Clinical Trials Register (SANCTR) and at clinicaltrials.gov. Both stents being compared in this trial are already approved by the South African Health Products

Regulatory Authority (SAHPRA), and as they form part of standard of care, application to SAHPRA will not be necessary.

Participants

Eligibility criteria for trial participants:

Inclusion Criteria (all criteria must be met):

- Adult patients 18 years of age or older
- Informed consent obtained from the patient after oral and written explanation of the trial
- Histologically confirmed malignancy of the distal oesophagus or OGJ
- Obstructive or irresectable malignancy due to metastases, local tumour infiltration or poor performance status

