- Once deployed, the distal end of the stent must have crossed the OGJ junction and be lying within the proximal stomach

Exclusion Criteria:

- Patient declining or unable to give informed consent, including inability to speak or understand either English, Afrikaans or isiXhosa.
- Patient unable to comply with the follow-up protocol of the trial (e.g. does not have a contactable telephone number)
- Oesophageal cancers selected for curative treatment or irresectable oesophageal cancers selected for palliative chemoradiation, but not requiring oesophageal stenting
- Benign oesophageal pathology or extrinsic compression of the oesophagus from another cause
- Patients with oesophageal cancers where the stent does not cross the OGJ
- Pregnant patients
- Patient performance status precluding any intervention or sedation

Setting and Location of Trial

This trial will take place at the Upper Gastrointestinal Surgery Unit at Groote Schuur Hospital (GSH). All stent insertions for the trial will be performed by either of the two full-time consultants working in the Upper Gastrointestinal Surgery Unit at GSH. Palliative oesophageal stenting is performed in the endoscopy suite in E23 under conscious sedation. After appropriate post-procedural observation in the unit, the patient will be admitted to the hospital for overnight observation and if deemed well enough, will be discharged home the following day after the scintigraphy.

Interventions

Patients considered eligible for the trial will be enrolled after obtaining informed consent. Oesophageal stenting will be performed according to standard practices at the GSH endoscopy suite using video endoscopy (standard gastroscope) and fluoroscopy. Patients will be appropriately sedated for the procedure, provided with supplemental oxygen and a diagnostic upper gastrointestinal endoscopy will then be performed to confirm the site and length of the histologically confirmed oesophageal cancer. Randomisation will then occur only if stenting is required which will result in OGJ overlap. Regardless of which type of stent the patient receives, all enrolled participants will be prescribed a twice daily dose of a proton pump inhibitor post the procedure, which is continued indefinitely as per the current standard of care at GSH.

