Using a power calculation for comparison of two continuous data means in a superiority assessment (with GerdQ score means as the primary outcome assessed), assuming a 2-point reduction in GerdQ mean score between the two groups - mean GerdQ score of 9 in the conventional stent control group and a GerdQ score of 7 in the anti-reflux stent group - with a standard deviation of 3, with an alpha level of 5% and power set at 80%, a sample size of 72, with 36 in each arm, is required.

Correlating this to the previous randomised controlled trials, it is noted that these numbers are similar, but slightly higher than previous trials. With concerns that a number of these previous trials were underpowered, a slightly bigger sample size is deemed appropriate.

Time Frame

The study will begin as soon as HREC approval has been granted and the relevant registrations with SANCTR and clinicaltrials.gov have been completed. It is expected to run for 36 months. Interim analyses of the collected data will be performed at 12 and 24 months.

Budget

All research-related costs will be covered by the General Surgery and Surgical Gastroenterology Research Funds.

1. Stents:

Both types of oesophageal stents (conventional and anti-reflux) are currently available at Groote Schuur Hospital and as they form part of the standard treatment of these patients, will not need to be purchased specifically for this research study.

- Scintigraphy: R4000 per investigation x 72 patients = R288 000
- 3. Clinical coordinator:

The clinical coordinator for this trial is already employed by the University of Cape Town and is very active in multiple research projects within the Surgical Gastroenterology Unit. She will thus not need to be renumerated specifically for her assistance in this trial.

4. Other Costs:

This trial will not require specific electronic or other research-related equipment or major stationary costs. All other minor costs will be borne by the study investigators.

TOTAL COSTS:

R288 000

REFERENCES

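### The 36 per arm assumes a GerdQ score from every patient, and the stated 80% power is tied to no defined analysis; an unadjusted week-8 comparison would have roughly 57-63% if the quoted median survivals ran from stenting.

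*Combined protocol and SAP*

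**What the plan says.** The Sample Size section takes mean GerdQ scores of 9 and 7, SD 3, and concludes that "with an alpha level of 5% and power set at 80%, a sample size of 72, with 36 in each arm, is required". It makes no allowance for loss, and the scintigraphy budget also counts exactly 72 patients.

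On the outcome, "The primary outcome will be patient-reported rates of symptomatic volume GOR and objectively measured volume GOR in both study groups". GerdQ is taken at baseline, and then "Patients will be phoned at 1, 2, 4 and 8 weeks post stent insertion". The Primary Outcome Measure section says only that group means can be compared. The Statistical Analysis section says only that inferential statistics will be used. Neither names a visit, a summary over visits, a model, a baseline adjustment or a rule for patients who die.

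On prognosis, the opening background section gives "median survival from the time of diagnosis being only 15 weeks", and 75 days (10.7 weeks) for complete obstruction. The Follow-up section adds: "Patients with palliative oesophageal cancer are in most instances frail and have a significantly limited life expectancy".

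On survival data, the Data Collection list and Appendix 7 record status at 8 weeks only, while the Statistical Analysis section plans Kaplan-Meier curves.

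**The concern.** A patient who has died has no GerdQ score. With the survival the protocol quotes, an appreciable share of patients may be gone by the last call, yet the calculation treats all 36 per arm as evaluable. The text permits anything from an unadjusted week-8 test to a joint analysis of four visits, and these differ widely in power.

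A team that tested week-8 means could miss a true 2-point benefit about 4 times in 10, where the protocol implies 2 in 10. The Sample Size section itself justifies the trial's size by concern that earlier trials were underpowered.

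**Working it through.** **Inputs from the protocol.** Difference 2, SD 3 (so d = 2/3), alpha 5%, power 80%, 36 per arm (Sample Size); visits at weeks 1, 2, 4 and 8 (Follow-up); medians of 10.7 and 15 weeks (background).

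**Assumptions, not in the protocol.** Time origin at stenting, survival shape, equal survival in both arms, missed-call rate, within-patient and baseline correlations, any alpha split, and a constant 2-point effect.

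**1. The plan's own figure.** n per arm = 2 × (1.96 + 0.8416)² × 9/4 = 35.3, rounded up to 36. Power at 36 per arm is 79.7% (noncentral t) or 80.7% (normal approximation). A one-sided test would need only 28, so the plan used a two-sided test on complete data with no inflation.

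**2. Loss at one visit, no survival model.** Unadjusted t-test with 36 × (1 − loss) per arm:

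| Loss | 10% | 20% | 30% | 40% |
|---|---|---|---|---|
| Power | 75.2% | 70.1% | 64.0% | 57.1% |

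**3. Exponential survival from stenting, deaths only.** S(w) = 2^(−w/median), n = 36 × S(w). By week 8, 31% (median 15) to 40% (median 10.7) have died.

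| Week | n per arm, medians 10.7 / 15 | Power |
|---|---|---|
| 1 | 33.7 / 34.4 | 77.0 / 77.8% |
| 2 | 31.6 / 32.8 | 74.2 / 75.8% |
| 4 | 27.8 / 29.9 | 68.4 / 71.8% |
| 8 | 21.4 / 24.9 | 56.8 / 63.4% |

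If a further 10% of week-8 calls were missed, week 8 would be about 52 / 59%.

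**4. Sensitivity at week 8, deaths only.** Weibull shape 0.75 gives 55.1 / 60.6% and shape 1.5 gives 59.9 / 68.0% at the same medians. Exponential medians of 20 and 26 weeks give 67.6% and 70.5%.

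**5. Single visit with baseline adjustment.** The SD is multiplied by √(1 − r²), with one degree of freedom fewer. At r = 0.3, week 1 is 80.7 / 81.5% and week 8 is 60.8 / 67.5%. At r = 0.5, week 4 is 80.4 / 83.3% and week 8 is 69.1 / 75.8%.

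**6. All four visits together.** Working independence with visit effects and a robust variance; true correlation ρ between any two visits; a share p = 0.9 of calls answered; no baseline credit. Let M be the number of scores a patient gives and S₁ to S₄ survival at the four visits.

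- E(M) = p(S₁ + S₂ + S₃ + S₄)
- E(M²) = E(M) + 2p²(S₂ + 2S₃ + 3S₄)
- Variance per arm = 9 × [(1 − ρ)E(M) + ρE(M²)] / [36 × E(M)²]
- Power = Φ(2/√(2 × variance) − 1.96)

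Example, median 15 and ρ = 0.7: E(M) = 3.050, E(M²) = 10.578, variance = 0.2236, standard error = 0.669, power = 84.9%.

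| Power, medians 10.7 / 15 | ρ = 0.5 | ρ = 0.7 | ρ = 0.9 |
|---|---|---|---|
| Normal approximation | 89.9 / 91.1% | 83.4 / 84.9% | 77.1 / 78.6% |
| Small-sample-corrected errors (simulation) | 89.0 / 90.0% | 82.8 / 84.4% | 76.0 / 77.5% |
| Normal, alpha 2.5% | 84.0 / 85.6% | 75.5 / 77.3% | 67.7 / 69.5% |
| Normal, baseline correlation 0.3 | 93.7 / 94.6% | 87.6 / 88.8% | 81.1 / 82.5% |

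The simulation row uses 10,000 trials per cell, the Kauermann-Carroll correction and t on 70 degrees of freedom. Its type I error was 4.6-5.3%, against 5.5-6.2% uncorrected. No figure includes the interim analyses planned at 12 and 24 months.

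**The case against.** The sample-size arithmetic is correct, and no section makes week 8 the primary visit. A score at every call followed by a comparison of means can equally be read as an all-visit analysis, so quoting week 8 picks the least favourable option. This is fair: the week-1 shortfall is trivial, and a joint analysis can reach 80% or more with the same 72 patients.

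The survival inputs are also weak. The 15-week median runs from diagnosis, and the shorter one covers complete obstruction, whereas the trial admits "Obstructive or irresectable malignancy due to metastases, local tumour infiltration or poor performance status" and excludes "Patient performance status precluding any intervention or sedation". No survival from stenting is given. This stands too, and is why the week-8 figure is conditional. It still spans only 55-71% across the survival assumptions tried, counting deaths alone.

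Other remedies are defensible. Keeping 36 evaluable per arm at week 8 would take 53 to 61 randomised per arm (36/0.691 and 36/0.596), or 106 to 122 in total before missed calls. A prespecified early visit is another choice. As to dates, prospective entry at each contact might bracket a death between two calls, but no listed field supplies its date.

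None of this removes the two omissions: the protocol states neither an attrition allowance nor the analysis to which the 80% applies.

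**Conclusion.** The concern holds. The 36 per arm is a complete-data figure with no margin, and the 80% is attached to no defined GerdQ analysis; neither statement needs a survival assumption. The size of the shortfall does. For an unadjusted single-visit test with medians of 10.7-15 weeks from stenting and exponential survival, it is negligible at week 1, material from about week 4, and reaches 57-63% power at week 8.

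It would be wrong to call the trial underpowered under every analysis. Pooling the four visits keeps power near or above 80%, except at high within-patient correlation without baseline adjustment, or if alpha is split between the two primary measures. The point concerns GerdQ only, not the day-1 scintigraphy.

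**What to change.** Keep 72 patients and make three changes.

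1. **Define the primary GerdQ comparison** as the baseline-adjusted difference between arms over weeks 1, 2, 4 and 8 while alive. Use an estimator that matches that target, for example working independence with robust standard errors and a small-sample correction. Report survival by arm beside it.
2. **Replace the 80% statement** with the power of that analysis under stated attrition, correlation and alpha assumptions, including any alpha split for the two primary measures and the interim analyses. The four-visit table above can serve as a guide. Say that an unadjusted comparison at a later single visit, especially week 8, has well under 80% power under these assumptions; do not say so of every single-visit comparison.
3. **Add date of stent insertion and date of death or last contact** to the data sheet, so that deaths can be told from missed calls and the Kaplan-Meier curves have event times.

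The cost is rewording two paragraphs and adding two date fields in REDCap, with no extra patients or visits. The estimate becomes an average over visits while alive rather than a week-8 effect. The stated power becomes conditional and may fall below 80% at high within-patient correlation (a baseline correlation of 0.3 would offset this at full alpha) or if alpha is split.
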